4.2. Scientific Rationale for Study Design

See Section 2.1.

4.2.1. Diversity of Study Population

Reasonable attempts will be made to enroll participants with the distribution of characteristics to ensure that the study population is representative of the population that will use RSVpreF in clinical practice.

4.3. Justification for Dose

The dose and formulation plan for this study is to start with 120 µg RSVpreF without any adjuvants in participants 5 to <18 years of age, before initiating the 60-µg dose level.

The FIH study in adults 18 through 85 years of age evaluated the safety, tolerability, and immunogenicity of 3 escalating RSVpreF dose levels of 60 μg, 120 μg, and 240 μg, with or without Al(OH)₃, when administered alone or concomitantly with SIIV (Study C3671001).

A study in older adults 65 through 85 years of age evaluated the safety, tolerability, and immunogenicity of 60-μg, 120-μg, and 240-μg RSVpreF doses formulated with Al(OH)₃ or a CpG/Al(OH)₃ adjuvant, or 240 μg RSVpreF with RSV antigens alone, when administered concomitantly with SIIV (Study C3671002).

A Phase 3 study in adults 65 years of age and older evaluated the safety, tolerability, and immunogenicity of 120 μg RSVpreF when administered concomitantly with SIIV (Study C3671006).

A study in healthy adults 18 through 50 years of age evaluated the safety, immunogenicity, and efficacy of 120 µg RSVpreF in a virus challenge model (NCT04785612).

4.4. End of Study Definition

The end of the study is defined as the date of the last visit of the last participant in the study.

A participant is considered to have completed the study if he/she has completed all periods of the study, including the last visit.

5. STUDY POPULATION

This study can fulfill its objectives only if appropriate participants are enrolled, including participants across diverse and representative racial and ethnic backgrounds. If a prescreening tool is utilized for study recruitment purposes, it will include collection of information that reflects the enrollment of a diverse participant population including, where permitted under local regulations, age, sex, race, and ethnicity. The following eligibility criteria are designed to select participants for whom participation in the study is considered appropriate. All relevant medical and nonmedical conditions should be taken into consideration when deciding whether a particular participant is suitable for this protocol.

Prospective approval of protocol deviations to recruitment and enrollment criteria, also known as protocol waivers or exemptions, is not permitted.

5.1. Inclusion Criteria

Participants are eligible to be included in the study only if all of the following criteria apply:

Age and Sex:

1. Participants 2 to <18 years of age at enrollment (signing of the ICD or providing assent to participate) at Visit 1.

Disease Characteristics:

- 2. Participants 2 to <18 years of age should either be healthy or be considered by the investigator to be at high risk of RSV disease based on the presence of 1 of the following chronic medical conditions^{9,10,25}:
 - Cystic fibrosis
 - Medically treated asthma
 - Other chronic respiratory diseases and malformations of the lung
 - Down syndrome
 - Neuromuscular disease
 - Cerebral palsy

• Hemodynamically significant or symptomatic congenital heart disease

Details of the chronic medical conditions listed above are further defined in the investigator site file.

Other Inclusion Criteria:

- 3. All participants 2 to <5 years of age must be seropositive for RSV as confirmed by serology.
- 4. Participants' parent(s)/legal guardian(s) and participants, as age appropriate, who are willing and able to comply with all scheduled visits, investigational plan, laboratory tests, and other study procedures. Participants' parent(s)/legal guardian(s) should be available for telephone contact with site staff for the duration of the study.
- 5. The participant's parent(s)/legal guardian is capable of giving signed informed consent as described in Section 10.1, which includes compliance with the requirements and restrictions listed in the ICD and in this protocol. Depending on the age of the participant and according to local requirements, participants will also be asked to provide assent as appropriate (verbal or written).

5.2. Exclusion Criteria

Participants are excluded from the study if any of the following criteria apply:

Medical Conditions:

- 1. Immunocompromised individuals associated with known or suspected immunodeficiency, as determined by history and/or laboratory/physical examination.
- 2. Individuals with a history of autoimmune disease or an active autoimmune disease requiring therapeutic intervention, including but not limited to systemic lupus erythematosus. Note: Stable type 1 diabetes and hypothyroidism are permitted.
- 3. Other medical or psychiatric condition including recent (within the past year) or active suicidal ideation/behavior or laboratory abnormality that may increase the risk of study participation or, in the investigator's judgment, make the participant inappropriate for the study.
- 4. History of severe adverse reaction associated with a vaccine and/or severe allergic reaction (eg, anaphylaxis) to any component of the study intervention(s).
- 5. Bleeding diathesis or condition associated with prolonged bleeding that would, in the opinion of the investigator, contraindicate intramuscular injection.
- 6. Individuals with a history of epilepsy or other seizure disorders, or a history of seizures and/or other neurological complications following vaccination.

Prior/Concomitant Therapy:

- 7. Previous vaccination with any licensed or investigational RSV vaccine or planned receipt during study participation. Children who may have been exposed to investigational RSV vaccines through maternal immunization will be permitted.
- 8. Receipt of investigational or approved monoclonal antibodies against RSV within 6 months before study intervention administration, or planned receipt throughout the study.
- 9. Receipt of blood/plasma products or immunoglobulins within 28 days before study intervention administration, or planned receipt throughout the study.
- 10. Receipt of chronic systemic treatment with known immunosuppressant medications (including cytotoxic agents or systemic corticosteroids), or radiotherapy, within 60 days before study intervention administration, or planned receipt throughout the study.

Note: Systemic corticosteroids are defined as those administered for ≥ 14 days at a dose of ≥ 20 mg/day of prednisone or equivalent (eg, for cancer or an autoimmune disease). Inhaled/nebulized, intra-articular, intrabursal, or topical (skin, eyes, or ears) corticosteroids are permitted.

Prior/Concurrent Clinical Study Experience:

11. Participation in other studies involving study intervention within 28 days prior to study entry and/or for the duration of study participation.

Diagnostic Assessments:

Not applicable.

Other Exclusion Criteria:

12. Investigator site staff directly involved in the conduct of the study and their family members, site staff otherwise supervised by the investigator, and sponsor and sponsor delegate employees directly involved in the conduct of the study and their family members.

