Because of the history of vaccine-mediated RSV disease enhancement following immunization of RSV-naïve infants in the 1960s with an FI-RSV,²² this study will be limited to seropositive children only and will assess T-cell responses to RSVpreF, specifically the Th1/Th2 profile. Unlike the FI-RSV vaccine, RSVpreF is an F glycoprotein subunit stabilized in the prefusion conformation and thus elicits a high ratio of neutralizing to nonneutralizing antibodies more closely matching the profile in naturally exposed individuals where no disease enhancement has been observed. Furthermore, the vaccine has already shown efficacy in preventing LRTI and severe LRTI in older adults and severe LRTI in infants born to vaccinated mothers (refer to Section 2.2.1). Available evidence indicates that RSVpreF is efficacious and is unlikely to confer any risk of enhanced disease.

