4. STUDY DESIGN

4.1. Overall Design

This is a Phase 1, open-label, age-descending, dose-finding study of the safety, tolerability, and immunogenicity of RSVpreF in RSV-seropositive children 2 to <18 years of age. Participants will be divided into 2 age strata: 5 to <18 years and 2 to <5 years. All participants will receive 1 dose of RSVpreF.

A single dose of RSVpreF 120 μg will be administered to the older age stratum first. Upon confirmation of an acceptable safety assessment by the IRC, dose administration will proceed in the 2- to <5-year age stratum with 60 μg . Pending IRC approval, the younger age stratum will receive 120 μg of vaccine. The IRC may also request that a dose of RSVpreF 60 μg be given in the older age stratum.

Dependent upon safety and/or immunogenicity data generated during the course of this study, it is possible that dose levels may not be started, may be terminated early, and/or may be added with dose levels below the lowest stated dose.

Stopping rules will apply as detailed in Section 8.3.5.

All participants within the 2- to <5-year age stratum will require a blood sample to be taken at the screening visit to assess serostatus, and only those who are seropositive can be enrolled and administered RSVpreF on Day 1. All participants 5 years of age and older will be considered RSV seropositive and will not require a screening test.

All participants will have blood drawn prior to vaccination on Day 1 and 1 month after vaccination to assess immune response elicited after vaccination with RSVpreF. An additional whole blood sample will be obtained prior to vaccination on Day 1 and 1 month after vaccination for PBMC isolation. An analysis of prespecified cytokines will be conducted to describe postvaccination cell-mediated immune responses 1 month after vaccination.

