5.4. Screen Failures

Screen failures are defined as participants who consent to participate in the clinical study but are not subsequently enrolled in the study. A minimal set of screen failure information is required to ensure transparent reporting of screen failure participants to meet the CONSORT publishing requirements and to respond to queries from regulatory authorities. Minimal information includes demography, screen failure details, and any SAEs.

Individuals who do not meet the criteria for participation in this study (screen failure) may be rescreened under a different participant number.

5.5. Criteria for Temporarily Delaying Enrollment/Randomization/Administration of Study Intervention

The following conditions may allow a participant to be vaccinated once the conditions have resolved and the participant is otherwise eligible:

- Current febrile illness (temperature ≥38.0°C [≥100.4°F]) or other acute illness within 48 hours before study intervention administration.
- Receipt of any live vaccine within 28 days before study intervention administration. Receipt of any nonlive vaccine (including COVID-19 vaccines authorized for temporary or emergency use) within 14 days before study intervention administration.
- Anticipated receipt of any nonstudy vaccine within 14 days after study intervention administration at Visit 1 (before Day 15).
- Receipt of short-term (<14 days) systemic corticosteroids (equivalent of ≥20 mg/day of prednisone). Study intervention administration should be delayed until systemic corticosteroid use has been discontinued for at least 28 days. Inhaled/nebulized, intra-articular, intrabursal, or topical (skin, eyes, or ears) corticosteroids are permitted.

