9.5. Sample Size Determination

Phase 1 enrollment is not based on a statistical criterion.

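### A child who tests RSV-seronegative before age 5 can be rescreened at 5 and deemed seropositive untested, because no rule carries the negative result forward

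*Protocol*

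**What the plan says.** - **Purpose of the restriction.** Protocol 2.2 recalls enhanced disease after vaccination of RSV-naive infants in the 1960s and concludes that "this study will be limited to seropositive children only and will assess T-cell responses to RSVpreF, specifically the Th1/Th2 profile". The risk table in 2.3.1 lists the restriction as a mitigation for that theoretical risk, and the synopsis gives the same reason.
- **Ages 2 to <5.** Inclusion criterion 3 (5.1): "All participants 2 to <5 years of age must be seropositive for RSV as confirmed by serology". No assay, antigen or cutoff is named.
- **Ages 5 and over.** Protocol 4.1: "All participants 5 years of age and older will be considered RSV seropositive and will not require a screening test". Protocol 8.10.1 and SAP 3.4.2 repeat the rule.
- **Rescreening.** Protocol 5.4: "Individuals who do not meet the criteria for participation in this study (screen failure) may be rescreened under a different participant number". Section 10.1.3 requires a new consent (and assent where applicable) at rescreening. Inclusion criterion 1 takes age at enrollment, that is, at consent or assent at Visit 1.
- **Passive antibody.** Exclusion 9 (5.2) bars "Receipt of blood/plasma products or immunoglobulins within 28 days before study intervention administration, or planned receipt throughout the study", and 6.9.1 repeats the 28 days. Exclusion 8 bars "Receipt of investigational or approved monoclonal antibodies against RSV within 6 months before study intervention administration".
- **Timing of the sample.** Section 8.10.1 foresees screening and vaccination on different days and states no maximum interval.

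**The concern.** In the younger stratum the protocol establishes seropositivity by a test. In the older stratum it presumes it from age. Each rule is clear alone. Together with an unrestricted rescreening rule, they let the presumption replace a negative result that the study itself obtained. The restriction exists to keep RSV-naive children from being vaccinated, and a child with a documented negative result is the one for whom the age-based presumption is weakest. What is at stake is agreement between the eligibility rules and the stated safeguard. No study estimate depends on it to any material degree.

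A related question is what the serostatus test measures. If passive antibody from a recent blood product could make it positive, the result would not show past infection. The documents allow that question to be asked but not answered.

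**Working it through.** There is no design figure to reproduce: Protocol 9.5 says "Phase 1 enrollment is not based on a statistical criterion". The check is mainly a reading of the rules in sequence.

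**1. The rescreening path**

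1. A child aged 4 consents, is tested and is seronegative. Inclusion criterion 3 is not met, so the child is a screen failure.
2. Section 5.4 permits rescreening under another participant number. It sets no limit by reason for failure and does not mention earlier results.
3. After the fifth birthday a new consent is signed under 10.1.3. Age is taken at that signing, so inclusion criterion 3 no longer applies.
4. Sections 4.1 and 8.10.1 deem the child seropositive, and no test is done.
5. No exclusion in 5.2 refers to an earlier negative serostatus. If otherwise eligible, the child is vaccinated.

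**2. Can the older stratum still be open?** Under 4.1.2, the review that opens the younger stratum takes place once 10 to about 40 older children have been vaccinated at 120 µg, out of about 40 planned.

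- Review at 10: 40 − 10 = 30 places may remain at 120 µg.
- Review at 40: 40 − 40 = 0 remain.
- The optional 60-µg older group, if requested, adds about 40.

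These are places that could be open, not children expected to take this path.

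**3. Does anything else close it?**

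| Provision | Effect |
|---|---|
| Exclusion 3 (investigator judgment, laboratory abnormality) | Discretionary; does not name serostatus |
| Section 5 (weigh all relevant conditions) | Discretionary |
| Section 8.1 screening log; 5.4 screen-failure details | Record the failure; do not bind a later screening |

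None carries the result forward.

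**4. What the existing data could show.** Day 1 neutralizing titers (NT) are measured in all participants (Protocol 8.2.2), and SAP 3.2.1 and 3.3.1 already handle prevaccination values below LLOQ. SAP 6.5.1 does not count such participants aged 5 and over.

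**5. The 28-day window.** Let *d* be the days from blood product to vaccination and *s* the days from serostatus sample to vaccination. The product-to-sample interval is *d* − *s*. Exclusion 9 constrains *d* only, and no maximum is stated for *s*. With *d* = 29 and *s* = 7 (illustrative), the sample falls 29 − 7 = 22 days after the product. Section 8.10.1 also lists the serostatus test among the procedures for the day of vaccination, while providing for results that are not available that day.

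For scale, assume an IgG half-life of 21 to 35 days (not in the documents). The share of passive antibody left at day 29 is 0.5^(29/21) = 0.38 to 0.5^(29/35) = 0.56. A positive test requires starting amount × share remaining to exceed the assay cutoff. Neither the starting amount nor the cutoff is given, so the calculation cannot show that any child would test positive.

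**The case against.** The strongest reply is that this will rarely, if ever, happen. It needs a seronegative child close to a fifth birthday, a family willing to return, and an older stratum still enrolling although that stratum starts first. The child may have been infected in the interval. The earlier failure is on the screening log, and an investigator may decline the child. All of this stands and limits the weight of the point. It does not remove the gap, because the protections are discretionary and none mentions serostatus.

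A reader might also infer more than the documents support:

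- **That donor antibody defeats the safeguard.** The documents give no donor antibody amount, assay or cutoff. Planned receipt of blood products (exclusion 9) and immunodeficiency (exclusion 1) are already excluded.
- **That exclusions 8 and 9 contradict each other.** They cover different products, and 5.2 and 6.9.1 agree on 28 days for blood products. Different windows for different products are not an inconsistency.
- **That GMFR is materially biased.** On the half-life assumption above, passive antibody falls between Day 1 and Visit 3 (28 to 35 days) to 0.5^(35/21) = 0.32 to 0.5^(28/35) = 0.57 of its Day 1 level. One affected child in 20 changes the group GMFR, through decay alone, by a factor of 0.32^(1/20) = 0.94 to 0.57^(1/20) = 0.97, about 3% to 6%, in a descriptive analysis. An inflated baseline would add to this by an amount that the documents do not allow to be fixed.
- **That most of the study is affected.** The age-based presumption covers 40 to 80 of 60 to 120 participants, but that counts everyone under an openly stated rule, not children with an overridden negative result.

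**Conclusion.** The rescreening gap holds on the text alone, with no outside figure. Followed as written, the protocol can vaccinate a child whose only serostatus result in the study is negative, despite its statement that "this study will be limited to seropositive children only". The number of such children is likely to be very small and could be zero. The conclusion rests on two conditions: that the older stratum is still enrolling when the child turns 5, and that the investigator does not exclude the child on judgment. It shows unverified serostatus. It does not show that an RSV-naive child would be vaccinated.

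The blood-product window is a secondary question for the sponsor. What the text supports is limited: the window is anchored to vaccination rather than to the serostatus sample, and the gap between the two has no stated maximum. Severity is minor.

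**What to change.** 1. **Protocol 5.4 (main change).** Reconcile rescreening with the presumption for ages 5 and over. State that a negative RSV serostatus result obtained in this study carries over at rescreening, so that the presumption does not apply to that child. Cross-refer from 4.1 and 8.10.1. Cost: one sentence and two cross-references. Downside: a rare rescreened child would not be enrolled on the presumption alone.
2. **SAP 6.5.1 (optional).** Report how many participants aged 5 and over have a Day 1 NT below LLOQ, with a note that this is not the same as a negative screening test. Cost: one table line from samples already drawn.
3. **Protocol 5.2, 6.9.1 and 8.10.1 (check).** Confirm that the blood-product window is consistent with the purpose of the serostatus test, given the assay used and the permitted interval between sample and vaccination, and reconcile the statements in 8.10.1 on when the test is done. No particular window is proposed here.

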5.3. Lifestyle Considerations

There are no lifestyle restrictions required for the participants in this study.

All pregnancies discovered in female participants during the study participation, which begins after obtaining informed consent as described in Section 8.4.1, will be recorded in the CRF in addition to completing the EDP (Section 8.4.5.1) and EDB (Section 8.4.5.2) reporting processes.

5.4. Screen Failures

Screen failures are defined as participants who consent to participate in the clinical study but are not subsequently enrolled in the study. A minimal set of screen failure information is required to ensure transparent reporting of screen failure participants to meet the CONSORT publishing requirements and to respond to queries from regulatory authorities. Minimal information includes demography, screen failure details, and any SAEs.

Individuals who do not meet the criteria for participation in this study (screen failure) may be rescreened under a different participant number.

5.5. Criteria for Temporarily Delaying Enrollment/Randomization/Administration of Study Intervention

The following conditions may allow a participant to be vaccinated once the conditions have resolved and the participant is otherwise eligible:

- Current febrile illness (temperature ≥38.0°C [≥100.4°F]) or other acute illness within 48 hours before study intervention administration.
- Receipt of any live vaccine within 28 days before study intervention administration. Receipt of any nonlive vaccine (including COVID-19 vaccines authorized for temporary or emergency use) within 14 days before study intervention administration.
- Anticipated receipt of any nonstudy vaccine within 14 days after study intervention administration at Visit 1 (before Day 15).
- Receipt of short-term (<14 days) systemic corticosteroids (equivalent of ≥20 mg/day of prednisone). Study intervention administration should be delayed until systemic corticosteroid use has been discontinued for at least 28 days. Inhaled/nebulized, intra-articular, intrabursal, or topical (skin, eyes, or ears) corticosteroids are permitted.

6. STUDY INTERVENTION(S) AND CONCOMITANT THERAPY

Study interventions are all prespecified investigational and medical devices and other interventions (eg, surgical and behavioral) intended to be administered to the study participants during the study conduct.

For the purposes of this protocol, study intervention refers to RSVpreF.

6.1. Study Intervention(s) Administered

Study Intervention(s)				
Intervention Name	PF-06928316 (RSVpreF)			
Arm Name (group of participants receiving a specific vaccine or no vaccine)	Active vaccine group			
Unit Dose Strength(s)	120 μg and/or 60 μg			
Туре	Vaccine			
Dose Formulation	The active ingredients in RSVpreF are 2 stabilized RSV prefusion F antigens, in equal amounts from virus subgroups A and B, in a lyophilized dosage form for reconstitution. The RSVpreF formulation will contain 120 µg of the RSV prefusion F antigen. RSVpreF is supplied as a lyophilized white cake in a 2-mL glass vial, with a 13-mm lyophilization stopper, aluminum overseal, and flip-off cap. RSVpreF will be reconstituted by a diluent consisting of sterile water in a PFS. The lyophilized RSVpreF formulation contains excipients that, after reconstitution, will yield a solution as detailed in the IB. The fill volume of the RSVpreF vial and diluent PFS are designed such that the 120-µg vaccine dose is delivered by injecting the entire contents of the syringe. The 60-µg vaccine dose is delivered by injecting 0.25 mL of a graduated syringe content.			
Route of Administration	Intramuscular			
Use	Experimental			
IMP or NIMP/AxMP	IMP			
Sourcing	Provided centrally by the sponsor			
Packaging and Labeling	The vaccine will be packaged within cartons labeled by Pfizer or its designee in accordance with current guidelines and applicable local and legal regulatory requirements.			

Study Arms(s)		
Arm Title	Active vaccine	
Arm Type	Experimental	

